### 7.3 Enrollment Controls

Enrollment will be monitored to ensure no more than the specified number of subjects is enrolled. An electronic data capture (EDC) system will be used and the system will be monitored to ensure maximum enrollment is contained. All sites will be notified when enrollment is near the target. The electronic database will display a message announcing that target enrollment is reached.

## 8 Study Procedures

**STRYKER CONFIDENTIAL** - THIS DOCUMENT CONTAINS CONFIDENTIAL AND PROPRIETARY INFORMATION THAT IS THE PROPERTY OF STRYKER CORPORATION. NEITHER THIS DOCUMENT NOR THE INFORMATION HEREIN MAY BE REPRODUCED, USED, OR DISCLOSED TO ANY THIRD PARTY WITHOUT THE PRIOR WRITTEN CONSENT OF STRYKER CORPORATION.

## Trevo® Retriever Registry (China)

### 8.1 Written Informed Consent

A sample ICF is provided in **Appendix C** for the Investigator to prepare for use at the site. The written Informed Consent documents must be prepared in the language(s) of the potential subject population. The ICF must be approved by the Ethics Committee (EC) and a copy provided to Stryker Neurovascular. Modifications to the form must be approved by Stryker Neurovascular prior to implementation. The document version must be identified on the ICF to maintain version control.

Written Informed Consent must be obtained for all subjects prior to data entry into the Trevo Retriever Registry electronic database. The subject or the subject's legally authorized representative (LAR) will be asked to sign the ICF. Consent should be obtained pre-procedure but depending on subject's acuity the consent may be obtained up to seven days post-procedure. No data may be entered into the database until written consent has been obtained. In the absence of informed consent, an EC approved waiver of consent and executed data use agreement must be in place.

Study personnel should document the consent process in the subject's medical record per Good Clinical Practice (GCP). The subject or LAR is to be provided a copy of the signed ICF.

### 8.2 Pre-procedure Assessment

The following pre-procedure data will be collected:

- Confirmation that the subject meets the Inclusion/Exclusion criteria
- Demographics and medical history, including blood pressure and pre-stroke mRS
- Baseline Labs (PT, PTT, platelets, INR, glucose, pregnancy test if applicable)
- Baseline Medications
- Neurological examination including mRS and NIHSS assessments
- Determination of intracranial lesion location and if clot location is amenable for treatment utilizing the Trevo Retriever

### 8.3 Trevo Thrombectomy Procedure

Physicians should follow the most current IFU at all times with regards to the device compatibility, preparation and the recommended retrieval procedure. The Trevo thrombectomy procedure should be performed per the following general steps:

- Gain arterial access with 6F (or larger) Guide Catheter or BGC
- Place the appropriate Trevo Microcatheter distal to the clot
- Use of intermediate DAC for added support is optional
- Load the Trevo Retriever into the compatible Trevo Microcatheter using the insertion tool and advance to site of occlusion
- Pull back on the Trevo Microcatheter to unsheath the Trevo Retriever within the clot

**STRYKER CONFIDENTIAL - THIS DOCUMENT CONTAINS CONFIDENTIAL AND PROPRIETARY INFORMATION THAT IS THE PROPERTY OF STRYKER CORPORATION. NEITHER THIS DOCUMENT NOR THE INFORMATION HEREIN MAY BE REPRODUCED, USED, OR DISCLOSED TO ANY THIRD PARTY WITHOUT THE PRIOR WRITTEN CONSENT OF STRYKER CORPORATION.**

## Trevo® Retriever Registry (China)

- After deploying the Retriever within the clot, visualize strut expansion and allow sufficient time for clot integration into the Retriever (approximately 5 minutes)
- If using a BGC, inflate the balloon to arrest flow
- Slowly pull the Trevo Retriever and Trevo Microcatheter back as a unit
- As the Trevo Retriever and microcatheter are being removed, begin vigorous aspiration through the guide catheter until the Trevo Retriever is removed from the subject

NOTE: Do not perform more than six (6) retrieval attempts in the same vessel. This total number applies for any combination of retrieval devices.

Immediately after each retrieval attempt with the Trevo Retriever, perform biplane angiography in order to assess the vessel patency in the neurovascular tree that is being treated. The same angiogram orientation should be used before and after the Trevo Thrombectomy procedure to assess the reperfusion status of the vessel(s).

- If reperfusion has been successful with the Trevo Retriever (recommended modified TICI score in the territory treated is  $\geq 2b$ ) the Trevo thrombectomy procedure should be stopped and no further interventions performed.
- If reperfusion has not been successful with the Trevo Retriever continue with additional retrieval attempts (up to the maximum allowed per the IFU). At any time during the procedure, adjunctive treatment (rescue therapy) may be initiated if deemed appropriate by the treating physician.

NOTE: The Trevo thrombectomy procedure should be terminated if any of the following occur:

- Neurological deterioration or alteration in function is detected leading to the suspicion of an intracranial hemorrhage.
- Evidence of intracranial hemorrhage on imaging is noted.
- The occlusion is refractory to six retrieval attempts in a single vessel.

Neurological deterioration or alteration in function leading to the suspicion of an intracranial hemorrhage will necessitate an emergent head CT or MRI scan. At the discretion of the treating physician, this evaluation may also include angiography or other diagnostic tests to determine the etiology of the clinical alteration. Management of an intracranial hemorrhage will be performed according to each institution's usual practice.

### 8.4 24 hours (-6/+24) post procedure

The following data will be collected at 24 hours (-6/+24) post procedure:

- NIHSS (see **appendix G**)
- SAEs related to the device or procedure.

**STRYKER CONFIDENTIAL** - THIS DOCUMENT CONTAINS CONFIDENTIAL AND PROPRIETARY INFORMATION THAT IS THE PROPERTY OF STRYKER CORPORATION. NEITHER THIS DOCUMENT NOR THE INFORMATION HEREIN MAY BE REPRODUCED, USED, OR DISCLOSED TO ANY THIRD PARTY WITHOUT THE PRIOR WRITTEN CONSENT OF STRYKER CORPORATION.

## Trevo® Retriever Registry (China)

- For all subjects who expire prior to the 24 hours (-6/+24) assessment, available information regarding the primary cause of death and date/time of death will be recorded, as well as, whether the subject was made “do not resuscitate” (DNR) or “comfort care only” prior to expiration.

Any death or SAE must be reported to Stryker Neurovascular within 24 hours of becoming aware of the event(s).

### 8.5 Discharge/Day 5-7 (whichever comes first)

A subject may be discharged from the hospital when clinically stable, at the Investigator's discretion. The following data will be collected at between Day 5-7 (if patient remains in the hospital) or at Discharge, whichever occurs first:

- NIHSS (see **appendix G**)
- mRS (see **appendix F**)
- SAEs related to the device or procedure
- Subject disposition at time of discharge
- For all subjects who expire prior to the Day 5-7/Discharge assessment, available information regarding the primary cause of death and date/time of death will be recorded, as well as, whether the subject was made DNR or “comfort care only” prior to expiration.

Any death or SAE must be reported to Stryker Neurovascular within 24 hours of becoming aware of the event(s).

### 8.6 Post Discharge Follow-up

The designated staff at the clinical site will review the study requirements with the subject to maximize compliance with the follow-up schedule. The staff will instruct subjects to return for follow-up assessments according to the study Time and Events Schedule in **Appendix D**. Study staff should establish a date for the follow-up visits with the subject and if possible, schedule the visits at the time of hospital discharge.

The study will be considered complete after all subjects have completed the Day  $90 \pm 14$  follow-up assessments. Requirements of each follow-up evaluation are detailed below.

#### 8.6.1 Day 30 (+14)

At Day 30 (+14 days) the following study assessments should be performed:

- mRS (see **Appendix F**) - A telephone assessment is conducted
- SAEs related to the device or procedure
- For all subjects who expire prior to the Day 30 assessment, available information regarding the primary cause of death and date/time of death will be recorded, as well as, whether the subject was made DNR or “comfort care only” prior to expiration.

Any deaths or SAE must be reported to Stryker Neurovascular within 24 hours of becoming aware of the event(s).

**STRYKER CONFIDENTIAL** - THIS DOCUMENT CONTAINS CONFIDENTIAL AND PROPRIETARY INFORMATION THAT IS THE PROPERTY OF STRYKER CORPORATION. NEITHER THIS DOCUMENT NOR THE INFORMATION HEREIN MAY BE REPRODUCED, USED, OR DISCLOSED TO ANY THIRD PARTY WITHOUT THE PRIOR WRITTEN CONSENT OF STRYKER CORPORATION.

## Trevo® Retriever Registry (China)

### 8.6.2 Day 90 ( $\pm 14$ )

At Day 90 ( $\pm 14$  days) the following study assessments should be performed:

- mRS score (see **Appendix F**) - If subject is unable to return to the clinic for the Day 90 visit, a telephone mRS assessment is preferable to no assessment
- SAEs related to the device or procedure
- For all subjects who expire prior to the Day 90 assessment, available information regarding the primary cause of death and date/time of death will be recorded, as well as whether the subject was made DNR or “comfort care only” prior to expiration.

Any death or SAE must be reported to Stryker Neurovascular within 24 hours of becoming aware of the event(s).

## 9 Statistical Methods

### 9.1 Sample Size Estimate and Justification

There will be no sample size/or power estimation for this single-arm registry.

Two hundred subjects will be enrolled at up to 15 centers in China. Since recent positive data released from MR CLEAN and other stent retriever randomized trials, there are more research questions to be answered such as how the time to treat will affect the patient outcome and how image screening may contribute to patient selection. Data analysis will be performed under guidance from the Study PIs, Steering Committee, and Sponsor.

### 9.2 Analysis Populations

The Intent-to-treat principle will be followed to define the analysis population. All of the subjects who signed the informed consent and in whom Trevo Retriever was deployed through the microcatheter are considered enrolled and will be included in the analyses.

Sub-group analyses for the Registry will be performed under guidance from the Study PIs, Steering Committee, and Sponsor.

### 9.3 Statistical Analysis

All statistical analyses will be performed using SAS version 9.4 or above. (Copyright © 2002-2008 by SAS Institute Inc., Cary, North Carolina, USA, All rights reserved)

**STRYKER CONFIDENTIAL** - THIS DOCUMENT CONTAINS CONFIDENTIAL AND PROPRIETARY INFORMATION THAT IS THE PROPERTY OF STRYKER CORPORATION. NEITHER THIS DOCUMENT NOR THE INFORMATION HEREIN MAY BE REPRODUCED, USED, OR DISCLOSED TO ANY THIRD PARTY WITHOUT THE PRIOR WRITTEN CONSENT OF STRYKER CORPORATION.

## Trevo® Retriever Registry (China)

### 10 Data Management

#### 10.1 Data Collection and Processing

Data will be collected in a secure, password protected electronic data capture (EDC) system, which is accessible via the Internet. All pertinent data will be entered by trained study center personnel into the electronic Case Report Forms (eCRFs). A unique subject ID number will be assigned to each subject. Every reasonable effort should be made to complete data entry within one week of data collection. For adverse reporting requirements refer to section 14. Any data discrepancies may be queried during ongoing review of data by the sponsor or may be identified and queried during routine remote data review process. Remote data review may be performed to verify data accuracy and ensure queries are resolved. The Principal Investigator or Sub-investigator must ensure the accuracy and completeness of the recorded data and provide his/her electronic signature on the appropriate eCRF.

Images sent to a Core Lab may also be entered into a separate EDC system. The core lab will ensure no personally identifiable information is available to the sponsor. Ongoing data review will be performed to identify possible data discrepancies. Manual and/or automatic queries may be created in the EDC system and will be issued to Core Lab for appropriate resolution.

### 11 Monitoring

The Sponsor is responsible for monitoring all data collected at the site to verify that the rights and wellbeing of subjects are protected, that trial data are accurate (complete and verifiable to source data) and that the trial is conducted in compliance with the protocol, GCP and regulatory requirements.

Data will be monitored for completeness and logical consistency. De-identified procedure summary, anesthesia record, must have the Trevo Registry subject identification number recorded on any forms sent to Stryker Neurovascular. The de-identified procedure documents may be compared against the eCRFs to ensure consistency for each subject enrolled.

Stryker Neurovascular will conduct an assessment of each participating site to assure that the investigators understand the investigational plan, as well as, their obligations to conduct the registry in accordance with applicable Regulations, GCP's and the registry protocol. The monitor will also confirm that the investigator has an adequate subject population, facilities, personnel and time to conduct the registry properly. Periodic monitoring visits may be made to confirm that the site remains compliant with the protocol, applicable Regulations, GCP and that all agreed-upon activities are carried out by the investigator and other specified staff members.

It is important that the Investigator and relevant study site personnel are available during monitoring visits and that sufficient time is devoted to the process. In order to perform her or his role well, the monitor must be given access to primary subject medical records which support the registry eCRFs. This access must be disclosed to the subject via the informed consent.

The investigator agrees to complete all registry requirements within three months of written notice of study completion. Continuation of the registry beyond this time must be mutually agreed upon in writing by both the investigator and Stryker Neurovascular.

**STRYKER CONFIDENTIAL - THIS DOCUMENT CONTAINS CONFIDENTIAL AND PROPRIETARY INFORMATION THAT IS THE PROPERTY OF STRYKER CORPORATION. NEITHER THIS DOCUMENT NOR THE INFORMATION HEREIN MAY BE REPRODUCED, USED, OR DISCLOSED TO ANY THIRD PARTY WITHOUT THE PRIOR WRITTEN CONSENT OF STRYKER CORPORATION.**

## Trevo® Retriever Registry (China)

Stryker Neurovascular will conduct a registry closeout meeting with each Trevo Registry site after the final data query is generated and data requests are addressed. The purpose of the closeout meeting is to confirm that all registry-related activities are complete and site personnel are aware of the regulatory obligations following study closure activities. The closeout meeting may transpire remotely e.g. teleconference or at an on-site monitoring visit. The closeout activities include but are not limited to the following:

- Final regulatory document review and collection of any outstanding documents including a copy of the investigator notification letter sent to the EC regarding completion of the Trevo Retriever Registry
- Address and close any open action items
- Discuss record retention requirements
- Review publication guidelines

## 12 Auditing

Sites may be subject to a quality assurance audit by Stryker Neurovascular or its designees, or other regulatory authorities who must be allowed access to eCRFs, source documents, and other study files.

It is important that the Investigator and relevant study personnel are available during any audits and that sufficient time is devoted to the process. The Sponsor audit reports will be kept confidential.

## 13 Device Accountability

There will be no device accountability or tracking as the Trevo Retriever has regulatory authorization to market the device.

## 14 Adverse Events

The following adverse events will be reported:

- all adverse events that occur during the procedure
- all SAEs related to the device or the procedure through Day 90
- all serious adverse events that result in death through Day 90

### 14.1 Adverse Event Definitions and Classification

Term	Definition	Reference
Adverse Event (AE)	Any untoward medical occurrence in a subject. This definition does not imply that there is a relationship between the adverse event and the device under investigation.	ISO 14155-1

**STRYKER CONFIDENTIAL** - THIS DOCUMENT CONTAINS CONFIDENTIAL AND PROPRIETARY INFORMATION THAT IS THE PROPERTY OF STRYKER CORPORATION. NEITHER THIS DOCUMENT NOR THE INFORMATION HEREIN MAY BE REPRODUCED, USED, OR DISCLOSED TO ANY THIRD PARTY WITHOUT THE PRIOR WRITTEN CONSENT OF STRYKER CORPORATION.

## Trevo® Retriever Registry (China)

Term	Definition	Reference
Adverse Device Effect (ADE)	
Any untoward and unintended response to a medical device.
 
Note 1: This definition includes any event resulting from insufficiencies or inadequacies in the instructions for use or the deployment of the device.
 
Note 2: This definition includes any event that is a result of a user error.
	ISO 14155-1
Serious adverse event (SAE)	
An adverse event that:
 
 
• led to death
 
• resulted in a life-threatening illness or injury
 
• resulted in a permanent impairment of a body structure or a body function
 
• required in-subject hospitalization or prolongation of existing hospitalization
 
• resulted in medical or surgical intervention to prevent permanent impairment to body structure or a body function
 
• led to fetal distress, fetal death or a congenital abnormality or birth defect
 
	ISO 14155-1
Serious Adverse Device Effect (SADE)	An adverse device effect that has resulted in any of the consequences characteristic of a serious adverse event or that might have led to any of these consequences if suitable action had not been taken or if circumstances had been less fortunate.	ISO 14155-1
Unanticipated Adverse Device Effect (UADE)	Serious adverse device effect which by its nature, incidence, severity or outcome has not been identified in the current version of the risk analysis report	ISO 14155-1

Underlying diseases are not reported as AEs unless there is an increase in severity or frequency during the course of the registry. Death should not be recorded as an AE, but should be reflected as an outcome to a specific AE.

### 14.2 Relationship

The Investigator must assess the relationship of the AE to the study device using the following criteria categories and definitions:

Unrelated - The AE is due to a concurrent illness or effect of another device/drug and is not related to the study device.

Related - The AE is due to the study device (possible, probable, or highly probable).

**STRYKER CONFIDENTIAL** - THIS DOCUMENT CONTAINS CONFIDENTIAL AND PROPRIETARY INFORMATION THAT IS THE PROPERTY OF STRYKER CORPORATION. NEITHER THIS DOCUMENT NOR THE INFORMATION HEREIN MAY BE REPRODUCED, USED, OR DISCLOSED TO ANY THIRD PARTY WITHOUT THE PRIOR WRITTEN CONSENT OF STRYKER CORPORATION.

## Trevo® Retriever Registry (China)

Unknown - The temporal relationship between the AE and study device cannot be clearly determined.

The Investigator must assess the relationship of the AE to the index procedure using the following categories and definitions:

Unrelated - The AE is due to a concurrent illness or effect of a drug and is not related to the index procedure.

Related - The AE is due to the index procedure (possible, probable, or highly probable).

Unknown - The temporal relationship between the AE and index procedure cannot be clearly determined.

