**Ver AA**

4. Rate of study device and procedure related serious adverse events (SAE) through Day 90.

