**Ver AA**

**Table 12: All SAEs**

	# of events	Percentages of subjects with events* (Total subjects=xxx)
All SAEs		
Details of all SAEs	xx	xx.x% (xx/xxx)
...	xx	
...	xx	xx.x% (xx/xxx)
...	xx	xx.x% (xx/xxx)
Study device and procedure related SAEs		
Total	xx	xx.x% (xx/xxx)
Details of study device and procedure related SAEs	xx	xx.x% (xx/xxx)
...	xx	xx.x% (xx/xxx)
...	xx	xx.x% (xx/xxx)
...	xx	xx.x% (xx/xxx)
Study device related SAEs only		
Total	xx	xx.x% (xx/xxx)
Details of study device related SAEs	xx	xx.x% (xx/xxx)
...	xx	xx.x% (xx/xxx)
...	xx	xx.x% (xx/xxx)
...	xx	xx.x% (xx/xxx)
Procedure but not study device related SAEs		
Total	xx	xx.x% (xx/xxx)
Details of procedure but not study device related SAEs	xx	xx.x% (xx/xxx)
...	xx	xx.x% (xx/xxx)
...	xx	xx.x% (xx/xxx)
...	xx	xx.x% (xx/xxx)
Study device or procedure related SAEs		
Total	xx	xx.x% (xx/xxx)
Details of study device or procedure related SAEs	xx	xx.x% (xx/xxx)
...	xx	xx.x% (xx/xxx)
...	xx	xx.x% (xx/xxx)
Not study device and not procedure related SAEs		
Total	xx	xx.x% (xx/xxx)
Details of not study device and not procedure related SAEs	xx	xx.x% (xx/xxx)
...	xx	xx.x% (xx/xxx)
...	xx	xx.x% (xx/xxx)

\*: Some subjects may experience multiple events

STRYKER CONFIDENTIAL - THIS DOCUMENT CONTAINS CONFIDENTIAL AND PROPRIETARY INFORMATION THAT IS THE PROPERTY OF STRYKER CORPORATION. NEITHER THIS DOCUMENT NOR THE INFORMATION HEREIN MAY BE REPRODUCED, USED, OR DISCLOSED TO ANY THIRD PARTY WITHOUT THE PRIOR WRITTEN CONSENT OF STRYKER CORPORATION

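### Relatedness may be graded Unknown, but the related-SAE endpoint and its tables make no provision for that grade, and the collection scope for such SAEs is contradictory

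*Protocol*

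**What the plan says.** Protocol 14.2 requires a relatedness grade against the device and another against the index procedure, each on three levels. Related is broad: "Related - The AE is due to the study device (possible, probable, or highly probable"). Unknown is defined by timing. For the device it is "Unknown - The temporal relationship between the AE and study device cannot be clearly determined", and for the procedure "Unknown - The temporal relationship between the AE and index procedure cannot be clearly determined".

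Protocol 14 lists three kinds of event to report: "all adverse events that occur during the procedure", "all SAEs related to the device or the procedure through Day 90" and "all serious adverse events that result in death through Day 90". Section 14.3 restricts eCRF recording to fatal events and events related to device and procedure. The data lists in 8.4, 8.5, 8.6.1 and 8.6.2 ask for related SAEs, and the Appendix D footnote limits the period after the procedure to related SAEs and death. The same four visit sections also say, with no relatedness filter, that any death or SAE goes to the sponsor within 24 hours.

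The secondary safety endpoint in SAP 5.2.2 item 4 is "Rate of study device and procedure related serious adverse events (SAE) through Day 90". SAP 5.3 plans summaries of all SAEs by relatedness. Table 12 opens with all SAEs, then gives blocks for combinations of related grades, and ends with "Not study device and not procedure related SAEs". Table 13 has the same structure for events during the procedure. Neither has a row for Unknown. SAP section 8 describes the shells as samples that may change.

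**The concern.** The grading has three levels and the endpoint and its tables use two. The site that performed the open-label procedure assigns the grade. In the earlier single-arm TREVO study a clinical events committee adjudicated relationship; the sections available here describe no comparable step. The investigator's choice of grade therefore decides whether an SAE enters a named secondary safety endpoint.

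With no counting rule in advance, someone must choose one after the data are seen. The literal choice, counting only events graded Related, can lower the reported rate but never raise it. A second risk arises earlier: a site that follows section 14 and Appendix D has no instruction to record a non-fatal SAE after the procedure when its relationship is Unknown, and an event not recorded may not be recoverable at analysis.

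**Working it through.** The plan states no figure for this point, so there is nothing to reproduce. The check sets the passages side by side and then sizes one subject's effect.

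**Step 1: the grade combinations.** Two relations with three grades give 3 × 3 = 9 combinations. Taking the endpoint as related to the device or to the procedure:

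| Device grade (rows), procedure grade (columns) | Related | Unknown | Unrelated |
|---|---|---|---|
| Related | counted | counted | counted |
| Unknown | counted | no stated place | no stated place |
| Unrelated | counted | no stated place | not related |

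Five combinations carry at least one Related grade and count. One is Unrelated to both and belongs in the last block of Table 12. The other 9 − 5 − 1 = 3 combinations have no Related grade and at least one Unknown. They appear in the all-SAE block, if recorded, but in no relatedness block, unless read as not related.

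**Step 2: mixed grades.** An SAE graded procedure Related and device Unknown still enters the Table 12 block for either source. Under the shells, however, it would also appear among events related to the procedure but not to the device, a denial of device involvement that the investigator did not make.

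**Step 3: collection.**

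| Event | Protocol 14 and Appendix D | 24-hour reporting line in 8.4 to 8.6 |
|---|---|---|
| AE during the procedure, any grade | in scope | covered if serious |
| Fatal SAE through Day 90, any grade | in scope | covered |
| Non-fatal SAE after the procedure, Related | in scope | covered |
| Non-fatal SAE after the procedure, Unknown only | not in scope | covered |

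Only the last row is affected. There the sections conflict: section 14.3 and the visit data lists side with the middle column, and the 24-hour line says otherwise.

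**Step 4: size.** The denominator is 200 subjects (SAP section 4). A subject whose only qualifying SAE is Unknown moves the rate by 1/200 = 0.5 point.

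For a base rate, Protocol 2.1 gives 3/60 = 5.0% device-related and 5/60 = 8.3% procedure-related SAEs in TREVO. At 200 subjects these are 0.050 × 200 = 10 and 0.083 × 200 = 16.7, about 17. The number of Unknown subjects is an assumption. Exact (Clopper-Pearson) 95% intervals are in brackets:

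| Unknown-only subjects, counted as related | Base 10/200 | Base 17/200 |
|---|---|---|
| 0 | 5.0% (2.4 to 9.0) | 8.5% (5.0 to 13.3) |
| 2 | 12/200 = 6.0% (3.1 to 10.2) | 19/200 = 9.5% (5.8 to 14.4) |
| 4 | 14/200 = 7.0% (3.9 to 11.5) | 21/200 = 10.5% (6.6 to 15.6) |

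Four such subjects add 4 × 0.5 = 2.0 points on either base.

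**The case against.** A reader might infer that the plan removes Unknown SAEs from the rate. The documents do not support that as a stated rule. No sentence equates Unknown with not related, SAP 5.3 promises a summary by relatedness without excluding a level, and the shells may change. This stands: the defect is a missing rule, and exclusion is only what a literal count of related events would produce. Changeable shells make the repair easy but do not supply the rule.

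A reader might also infer that non-fatal Unknown SAEs never reach the sponsor. The 24-hour line in 8.4 to 8.6 prevents that conclusion. What remains is a contradiction about what is collected, and an event reported by that route still has no assigned place in the endpoint.

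It is fair to say, too, that Unknown may be rare. Possible causation already counts as Related, and Unknown covers only timing that cannot be determined. With NIHSS and CT/MR scheduled at 24 hours, and date and time of death recorded, timing will often be known. It would be tempting to apply an assumed Unknown share to the deaths expected from the earlier trials and quote a loss in points, but the documents offer no basis for any such share. The TREVO rates were also committee-adjudicated, so they are only a rough base for site-graded events.

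Finally, this is a descriptive registry with no hypothesis test or safety threshold, so no formal decision turns on the rate. That limits the severity. It does not remove the need to define a named secondary endpoint.

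**Conclusion.** The point holds in a limited form. Three of the nine grade combinations have no defined treatment in the related-SAE endpoint or in the relatedness blocks of Tables 12 and 13, and a literal count leaves them out, in the direction of a lower rate. Mixed Related and Unknown events still count, provided the endpoint means either source; if the wording in Table 11 means both at once they would be lost, but that is a separate labelling question. Mixed events would in any case be shown under a label that says more than the investigator did. The scope for non-fatal SAEs after the procedure graded Unknown is contradictory and must be reconciled.

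The size is 0.5 point per subject, assuming that the subject has no other counted SAE. The total cannot be known from the documents. The 2.0 points for four subjects is an illustration, and zero is possible. This is a cheap improvement, not a threat to the registry's main results.

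**What to change.** 1. In SAP 5.2.2 item 4 and Tables 11 to 13, state that an Unknown relationship is counted as related to that source. Show the number of Unknown events in its own row and give the rate without them as a supportive line. Reserve the last block of Table 12, and its counterpart in Table 13, for events graded Unrelated to both. Counting Unknown as related is a convention and assigns a cause the investigator left open; reporting both rates lets the reader see how much depends on it.
2. Reconcile the SAE scope across Protocol 8.4 to 8.6, 14, 14.3 and the Appendix D footnote, so that SAEs of related or unknown relationship are recorded on the eCRF.

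The cost is a sentence and some table rows in the SAP, and a protocol amendment that touches several sections with the same short change. The downside is a few more SAE records and a slightly higher stated rate. The collection change is best made early, since events left unrecorded may not be recoverable.
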